# 5.2 Pre-Treatment Criteria

The pre-treatment criteria for C1D1 and subsequent cycles is listed below:

- Adequate bone marrow, liver, and renal function according to the following criteria:

- Absolute neutrophil count ≥ 1,500 cells/mL ~ 1.5 K/µL
- Platelets  $\geq 100,000 \text{ cells/mL} \sim 100 \text{ K/}\mu\text{L}$
- $\circ \leq 1.5$  X institutional ULN **OR** Direct bilirubin  $\leq$  institutional ULN for subjects with total bilirubin levels > 1.5 institutional ULN
- Aspartate aminotransferase (AST)  $\leq 2.0 \text{ x ULN}$
- Serum creatinine level ≤ ULN or creatinine clearance ≥ 50 mL/min for participants with creatinine levels above normal limits (calculated by the Cockcroft-Gault formula)
- For women, a negative pregnancy test
- No intercurrent illness or medical condition that, in the opinion of the Investigator, may cause excess risk for the participant's continued treatment with the study drug

In any case of doubt or failure to meet the criteria listed above, the investigator should contact the Overall Principal Investigator, [name], and/or DFCI Neuro Oncology Coordinating Center for instructions on how to proceed with the treatment.

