#### 3.1 Inclusion Criteria

- **3.1.1** Histologically confirmed World Health Organization Grade IV malignant glioma (glioblastoma or gliosarcoma).
- **3.1.2** First or second progression of glioblastoma/gliosarcoma (according to RANO criteria) following standard of care treatment upon initial diagnosis with radiation.
- **3.1.3** Measurable disease by RANO criteria at progression.
- **3.1.4** The maximal tumor volume at baseline meets the following criteria as determined by a local site investigator or surgeon: Longest diameter  $\leq 4$ CM.
- **3.1.5** Surgically resectable disease at progression.
- **3.1.6** An interval of the following durations prior to randomization:
  - At least 28 days from prior surgical resection, or 7 days from stereotactic biopsy
  - At least 12 weeks from prior radiotherapy, unless there is unequivocal histologic confirmation of tumor progression
  - At least 23 days from prior chemotherapy
  - At least 42 days from nitrosureas
  - At least 42 days from other anti-tumor therapies (including vaccines)
  - At least 28 days from immune checkpoint blockade
  - At least 28 days or 5 half-lives from any investigational agent, whichever is shorter.

NOTE: no wash-out period required from TTF.

- **3.1.7** All clinically significant toxic effects of prior therapy must have recovered to grade 0 or 1 or pre-treatment baseline. Allowable exceptions are: alopecia, lymphopenia, and any laboratory value listed elsewhere in the inclusion criteria (provided it meets that criterion's requirements). Please contact the Overall Principal Investigator, [name], for questions regarding exceptions to this criterion.
- **3.1.8** Corticosteroid use at or less than dexamethasone 2mg daily. Participants should be on a stable or decreasing dose for at least 7 days prior to randomization.
- **3.1.9** Age  $\geq$  18 years on day of signing informed consent

- **3.1.10** KPS  $\geq$  70% (see Appendix A)
- **3.1.11** Adequate bone marrow, liver, and renal function according to the following criteria:
  - Absolute neutrophil count  $\geq$  1,500 cells/mL ~ 1.5 K/µL
  - Platelets  $\geq 100,000 \text{ cells/mL} \sim 100 \text{ K/}\mu\text{L}$
  - Total bilirubin  $\leq$  1.5 X institutional ULN **OR** Direct bilirubin  $\leq$  institutional ULN for subjects with total bilirubin levels > 1.5 institutional ULN
  - Aspartate aminotransferase (AST)  $\leq 2.0 \text{ x ULN}$

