### 6. DOSE DELAY

For patients who experience an adverse event possibly related to VB-111 and are scheduled for a repeat dose, the repeat dose will be delayed until they meet the criteria outlined in Section 5.2. No dose modifications are allowed.

For patients who experience an adverse event related to standard of care and are scheduled for a repeat dose, the repeat dose will be delayed until they meet the criteria outlined in Section 5.2. Dose reductions are permitted for standard of care therapies, at the discretion of the Investigator. We suggest up to two dose-reductions by 20% for each standard of care therapy.

Dosing interruptions are permitted in the case of medical/surgical events or logistical reasons not related to study therapy (e.g., elective surgery, unrelated medical events, participant vacation, and/or holidays). Participants should be placed back on study therapy within 3 weeks of the scheduled interruption, unless otherwise discussed with the Overall Principal Investigator, [name], or his designee. The reason for interruption should be documented in the participant's study record.

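### The neutrophil and platelet limits in criterion 3.1.11 and Section 5.2 each give two values that differ 1,000-fold, and the text does not say which governs

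*Combined protocol and SAP*

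**What the plan says.** Inclusion criterion 3.1.11 (Section 3.1) requires adequate marrow, liver and renal function. Its neutrophil limit reads "1,500 cells/mL ~ 1.5 K/µL", and its platelet limit equates 100,000 cells/mL with 100 K/µL.

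Section 5.2 repeats both limits. The neutrophil line is "Absolute neutrophil count ≥ 1,500 cells/mL ~ 1.5 K/µL", and the platelet line pairs the same two figures as in 3.1.11. Section 5.2 introduces its list with "The pre-treatment criteria for C1D1 and subsequent cycles is listed below", so the limits apply throughout post-surgery treatment as well as at entry.

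Section 6 refers back to that list. After an adverse event possibly related to VB-111, or one related to standard of care, "the repeat dose will be delayed until they meet the criteria outlined in Section 5.2". A separate paragraph of Section 6 covers interruptions for medical, surgical or logistical reasons not related to study therapy. It sets a three-week return period and does not cite Section 5.2.

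No other section defines the units or corrects them.

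**The concern.** Each line offers two numbers as the same threshold, and they are not the same threshold. A factor of 1,000 is far beyond anything the approximation sign could cover.

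The lines are rules that decide who enters and who is dosed. A reader who applies the figure printed first would pass practically any blood count, while a reader who applies the second would screen out low counts. The same participant could then be eligible and ineligible, or cleared for dosing and on hold, under one line of text. Appendix B Section 3.7.3 permits no eligibility exception without IRB approval, so the difference has procedural consequences too.

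The platelet limit has some practical bearing here. Section 7.1.1 lists thrombocytopenia and platelet decrease at 5-10% with VB-111. Table 1 allows lomustine or temozolomide in Group C, and Section 6 ties repeat doses delayed after a related adverse event to the same list. Neutropenia does not appear in the VB-111 frequency lists, so that argument does not extend to the neutrophil limit for VB-111.

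**Working it through.** **Inputs**

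- Neutrophils: 1,500 cells/mL, equated with 1.5 K/µL (3.1.11 and 5.2).
- Platelets: 100,000 cells/mL, equated with 100 K/µL (3.1.11 and 5.2).
- Conversion: 1 mL = 1,000 µL and 1 K = 1,000 cells, so K/µL = (cells/mL) / 1,000,000.

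**Trying to reproduce the stated equivalences**

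Neutrophils:
- From the first figure: 1,500 / 1,000 = 1.5 cells/µL, and 1.5 / 1,000 = 0.0015 K/µL. The plan states 1.5 K/µL.
- From the second figure: 1.5 × 1,000,000 = 1,500,000 cells/mL. The plan states 1,500 cells/mL.
- Ratio: 1.5 / 0.0015 = 1,000.

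Platelets:
- From the first figure: 100,000 / 1,000 = 100 cells/µL, and 100 / 1,000 = 0.1 K/µL. The plan states 100 K/µL.
- From the second figure: 100 × 1,000,000 = 100,000,000 cells/mL. The plan states 100,000 cells/mL.
- Ratio: 100 / 0.1 = 1,000.

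Neither equivalence reproduces, and the discrepancy is the same in both.

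**Where the mismatch comes from**

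If both sides are given the same volume unit, the numerals match: 1,500 / 1,000 = 1.5 and 100,000 / 1,000 = 100. The pattern is that of a volume unit differing between the two sides. It is not proof of which expression the sponsor meant.

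**Is it a fault of the PDF text?**

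Unlikely. The mismatch occurs four times (two limits in each of two sections), in both plain and formula text.

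**What the contradiction does to a decision**

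Take an assumed platelet count of 80 K/µL, for illustration only. In the first unit it is 80 × 1,000,000 = 80,000,000 cells/mL. Against the first figure it passes by a factor of 80,000,000 / 100,000 = 800. Against the second, 80 is below 100 and it fails. The same line gives opposite answers.

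**The case against.** The strongest reply is that this is a unit slip that can be seen on its face. Both expressions stand side by side, the numerals agree once the volume unit is the same, and a limit that excludes almost nobody cannot serve a criterion headed as adequate marrow function. This stands as a reason to expect few misapplications. It does not make the text consistent, and the choice between the figures remains the sponsor's to confirm.

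The documents also contain safeguards. Section 5.2 sends cases of doubt to the Overall Principal Investigator or the Coordinating Center. For entry, Section 4.1 has the ODQ review the checklist, and Appendix B Sections 3.7.1 and 5.1 have a Coordinating Center specialist check laboratory results before registration at other sites. These lower the risk, but none of them says which figure to check against.

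A reader might infer more than the documents support:

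- *That every delayed dose is released on these limits through Section 6.* Section 6 makes that link only for the two kinds of adverse-event delay. Its paragraph on unrelated interruptions does not.
- *That there is no haematological protection at all under the first figure.* The numeric screen would be empty, but Section 5.2 also excludes conditions that the investigator judges to carry excess risk, and Section 5.8 lists unacceptable adverse events and investigator decision as grounds for stopping. These are discretionary and do not replace a numeric limit, but they remain.
- *That all 45 planned evaluable participants are affected.* The criterion applies to all of them, but the number whose eligibility or dosing would change cannot be derived.
- *That a checklist or edit check already carries the cells/mL figure.* Neither the checklist nor the eCRF is in the documents, and nothing shows that any site has used that figure.

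**Conclusion.** The contradiction is real and exact: a factor of 1,000 in each of two limits, in each of two sections (0.0015 against 1.5 K/µL for neutrophils, 0.1 against 100 K/µL for platelets). It touches the numeric haematology threshold for entry, for C1D1 and later cycles, and for repeat doses delayed after an adverse event possibly related to VB-111 or related to standard of care.

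The arithmetic rests only on the definitions of the units. The view that practical risk is low rests on two assumptions: that most sites would read the K/µL figure, and that central review would do the same. Both are plausible, but the documents establish neither.

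Nothing statistical changes. The sample size, power, alpha, endpoints, analysis sets and the TIL analysis do not use these limits. The point should be fixed because the lines are decision rules and the correction is nearly free. There is no evidence of harm that would make it more urgent. Which limit is clinically right is not judged here.

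**What to change.** - The sponsor reconciles the two expressions and confirms which figure was intended for each limit.
- State each limit in one unit, with identical wording in 3.1.11 and 5.2. If a second expression is kept, derive it by correct conversion. Section 6 needs no change of its own, since it refers to 5.2.
- Check that the eligibility checklist and any eCRF edit checks use the same unit and value as the corrected text.

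The cost is four corrected lines (two limits in two sections) and one check of the checklist and eCRF. No analysis, sample size or schedule has to be reworked.

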### 5.3 Agent Administration

Trial treatment should be administered after all procedures/assessments have been completed as detailed on the Study Calendar (Section 10.0).

### 5.3.1 Pre-Surgery Dose Administration

VB-111/placebo must be administrated within 5 days from randomization.

**Group A:** Participants will receive VB-111  $1x10^{13}$  VPs by intravenous infusion  $21\pm7$  days prior to scheduled surgical resection.

**Group B**: Participants will receive placebo by intravenous infusion 21±7 days prior to scheduled surgical resection.

**Group C:** Participants will receive placebo by intravenous infusion 21±7 days prior to scheduled surgical resection.

### 5.3.2 Post-Surgery Dose Administration

For Group A and Group B, upon recovery from surgery (within 28-35 days after surgery), trial treatment should be administered after all procedures/assessments have been completed and reviewed as detailed on the Study Calendar (Section 10). Trial treatment may be administered up to 3 days before or after the scheduled infusion/injection day of each cycle due to administrative reasons.

All trial treatments should be administered on an outpatient basis. If the treating team would like to pursue treatment while inpatient, please contact the Overall Principal Investigator, [name], for prospective approval.

**Group A:** Participants will resume VB-111 every 6 weeks **Group B:** Participants will receive VB-111 every 6 weeks **Group C:** Participants will receive standard of care treatments

# 5.4 Trial Blinding/Masking

Pre-operative treatment will be blinded; therefore, the treating investigator and subject will not know whether VB-111 or placebo is administered. An unblinded pharmacist or designee not involved in other study assessments will prepare the Pre-operative study drug of VB-111/Placebo. Post-operatively, treatment will be unblinded.

# 5.5 Stratification

Randomization will be stratified according to baseline tumor size ( $\leq 15$  cc, >15 cc).

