- 19. Adverse events experienced by participants will be collected and recorded from the first dose of study treatment up to the 30-Day Post Drug Visit of the last dose of study medication (+ 7 days depending on when 30-Day Post Drug visit/contact occurs) and all SAEs (related and unrelated to trial treatment) up to 90 days after the last dose of treatment. Afterwards, report only SAEs that are considered related to trial treatment. Adverse events may also occur in screened participants during pre-allocation baseline period as a result of a protocol-specific intervention, including washout or discontinuation of usual therapy, diet, placebo treatment or a procedure.
- 20. For women of child bearing potential, a urine pregnancy test must be performed. If urine pregnancy results cannot be confirmed as negative, a serum pregnancy test will be required.
- 21. PT/INR, PT, PTT are required at screening and PTT will be checked again with pre-surgery labs. Thereafter,

coagulation to be checked when clinically indicated.

- 22. Hematology includes erythrocytes (RBC), hemoglobin, hematocrit, platelets, total WBC plus differential (neutrophils, lymphocytes, monocytes, eosinophils, basophils).
- 23. Serum Chemistry includes albumin, alkaline phosphatase (ALP), bicarbonate (HCO3), BUN, calcium, chloride, creatinine, glucose, magnesium, potassium, SGOT (AST), SGPT (ALT), sodium, total protein, total bilirubin.
- 24. Virology panel includes Hepatitis A Antibody, Hepatitis B Core IgG and M Antibody (Anti-HBC, total), Hepatitis B Surface Antibody (Anti-HBs), Hepatitis B Surface Antigen (HBsAg), Hepatitis C Surface Antibody (anti-HCV), HIV-1/2 Ag/Ab and HTLV-1/2 Ag/Ab. If any hepatitis serology is positive, qualitative PCR for Hepatitis B DNA or Hepatitis C RNA will be obtained and results must be negative for eligibility.
- 25. Imaging: gadolinium-enhanced contrast and non-contrast MRI. Initial imaging should be performed within 14 days prior to enrollment. On-study imaging should be performed every 6 weeks starting from post-surgery treatment Cycle 1 Day 1. The same imaging technique should be used in a participant throughout the trial, if feasible. Local reading (investigator assessment) will be used to determine eligibility and for participant management.
- 26. Response Assessment to be completed per RANO criteria (Section 10).

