#### 11.1.2 Measurable Disease

Measurable disease is defined as bi-dimensionally, contrast-enhancing, measurable lesions with clearly defined margins by MRI, with two perpendicular diameters of at least 10mm, visible on 2 or more axial slices which are preferably at most 5mm apart with 0mm skip. The presence of interslice gaps should be considered in determining the size of measurable lesions at baseline. Measurement of tumor around a cyst or surgical cavity should be considered non-measurable unless there is a nodular component measuring at least 10mm in diameter. The cystic or surgical cavity should not be measured in determining response.

All tumor measurements must be recorded in millimeters.

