## **11.1.4** Target Lesions

All measurable lesions up to a maximum of 5 lesions should be identified as target lesions and recorded and measured (sum of the products of the perpendicular diameters) at baseline. Target lesions should be selected on the basis of their size (lesions with the longest diameters) and their suitability for accurate repeated measurements by imaging techniques. Occasionally, the largest lesions may not be suitable for reproducible measurement and the next largest lesions which can be measured reproducibly should be selected.

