## 11.5 Radiology Review

The review of the baseline neuroimaging will be performed at DFCIto ensure the participants meet the inclusion criterial before the randomization. The review of on-study neuroimaging will be performed retrospectively at DFCI.

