## 13.3 Sample Size Consideration

This is a randomized, controlled, blinded, phase II, surgical trial to evaluate early immunologic pharmacodynamic parameters for the viral cancer therapy VB-111 in participants with surgically accessible recurrent/progressive glioblastoma (rGBM). Participants will be randomly assigned to group A or B or C with a 1:1: 1 randomization ratio prior to surgery. The primary hypothesis is that VB-111 can generate effective anti-tumor immune responses in the form of a statistically significant increase in TIL density comparing Group A (neoadjuvant/adjuvant) vs combined control group (Group B+C).

Based on our preliminary data, the mean of TIL density is estimated to be 0.4 (T cells per nucleated cell) (SD=0.5) in the combined control group (Group B and C). Comparing Group A vs Group B+C at an alpha level of 0.05 (1-sided) using a stratified two-sample t-test, a sample size of 30 in the combined Group (B+C), and 15 in Group A (Total of 45 evaluable) allows for the detection of a standard difference in TIL density of 0.8 or larger with 84% power. Effect size is defined as Cohen's D, the difference of two population means, divided by the pooled standard deviation. [63]

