## 13.4 Efficacy Analysis

A two-sample t-test with tumor size stratification will be used to test the difference of tumor infiltrating T cell density between the two groups (Group A vs combined Group B+C). Data distribution will be examined prior to analysis. Data transformations will be performed as deemed appropriate.

For the secondary endpoint of PFS6, historical comparison data are available from a pooled analysis of Phase II experience in recurrent Grade IV gliomas who have undergone surgery either just prior to starting treatment or as part of the protocol, which documented a PFS6 rate of 10%. Group comparisons (Group A vs C; Group B vs C; Group A+B vs C) will be conducted using the exact binomial test with Bonferroni adjustment to compare PFS6 rate at one sided alpha of 5%.

For OS, analyses will be conducted using historical comparison data which are available from a pooled analysis of Phase II experience in recurrent Grade IV gliomas who have undergone surgery either just prior to starting treatment or as part of. Kaplan-Meier (KM) curves and median estimates from the KM curves will be provided as appropriate. Participants without efficacy evaluation data or without survival data will be censored at Day 1. For evaluation of the expansion of TCR clones, a two-sample T-test with Bonferroni adjustment will be used to compare the increase number of expanded TCR clones after VB-111 in Group A+B vs Group C.

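### The primary TIL test uses baseline tumor size only as a two-level 15 cc split; adding continuous log volume would be a near-free gain in precision

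*Combined protocol and SAP*

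**What the plan says.** Section 5.5: "Randomization will be stratified according to baseline tumor size", in two levels divided at 15 cc. Section 13.3 sizes the trial on that basis: "Comparing Group A vs Group B+C at an alpha level of 0.05 (1-sided) using a stratified two-sample t-test", with 15 evaluable patients in Group A and 30 in B+C, a standardized difference of 0.8 and stated power of 84%. Section 13.4 repeats the test: "A two-sample t-test with tumor size stratification will be used to test the difference of tumor infiltrating T cell density between the two groups". No other baseline variable enters the primary analysis.

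Size is limited at entry by a diameter, although criterion 3.1.4 is worded as a volume: "The maximal tumor volume at baseline meets the following criteria as determined by a local site investigator or surgeon: Longest diameter" of at most 4 cm. Measurable disease (11.1.2) requires a lesion "with two perpendicular diameters of at least 10mm", and 11.1.4 allows several lesions: "All measurable lesions up to a maximum of 5 lesions should be identified as target lesions and recorded and measured".

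The plan does not say how cc are derived from the scan, whether several lesions are summed, which read supplies the volume, or what share of patients is expected above 15 cc.

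**The concern.** Eligibility is set in centimeters and stratification in cc, and the plan does not relate the two. A single lesion must be longer than about 3 cm, under a 4 cm limit, to pass 15 cc, so the upper stratum may be a minority, possibly a small one. Whatever its share, a two-level factor treats a tumor just over the cut like one of twice that volume, and a very small tumor like one just under the cut.

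What is at stake is precision. With only 15 patients in Group A, a baseline variable related to TIL density could tighten the primary comparison at almost no cost, and the plan already has to obtain this one before randomization.

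**Working it through.** **1. The plan's own power.** Inputs from 13.3: n = 15 and 30, d = 0.8, one-sided alpha 0.05. The noncentrality is 0.8 x sqrt(15 x 30/45) = 0.8 x 3.162 = 2.53 on 43 df, which gives 80.1%, and 80.1% again on 42 df with a stratum term. The stated 84% is not reproduced for 15 vs 30; an equal split of the 45 patients (22 vs 23) gives 84.0%. That is a separate matter, but it makes 80% the baseline for what follows.

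**2. Geometry of the cut.** Take one ellipsoidal lesion, volume = pi/6 x the product of its three axes.
- A sphere of 15 cc has diameter (6 x 15/pi)^(1/3) = 3.06 cm. A single lesion with a shorter longest diameter is always in the lower stratum.
- At 4 cm a sphere holds pi/6 x 64 = 33.5 cc. The other two axes must average (geometric mean) more than sqrt(15/33.5) = 67% of the longest to pass 15 cc.
- At 3.5 cm a sphere holds 22.4 cc, and the requirement is sqrt(15/22.4) = 82%.

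**3. Share above 15 cc.** The documents give no size or shape distribution, so everything here is assumed. The shorter axes are either equal to the longest (sphere) or drawn uniformly from the stated fraction of it up to 1.

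| Longest diameter | Sphere | 0.8 to 1 | 0.6 to 1 | 0.5 to 1 |
|---|---|---|---|---|
| Uniform 1-4 cm | 31% | 24% | 14% | 10% |
| Uniform 2-4 cm | 47% | 36% | 21% | 15% |
| Rising toward 4 cm | 53% | 42% | 25.5% | 18% |
| Peaked mid-range (two forms) | 20-23% | 11-14% | 5-7% | 3-4% |

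The range is about 3% to 53%, or roughly 2 to 24 of 45 patients; summing several lesions would raise it. At a true share of 10%, the chance of 5 or fewer patients above the cut is 71%; at 20% it is 9%.

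**4. Information kept by a split.** For a normal covariate with share p above the cut at z, the fraction of its explained variance retained is k = phi(z)^2/[p(1-p)], where phi is the standard normal density.
- p = 5%: 0.1031^2/0.0475 = 22%
- p = 15%: 0.2332^2/0.1275 = 43%
- p = 30%: 0.3477^2/0.21 = 58%
- p = 50%: 0.3989^2/0.25 = 64%

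No cut keeps more than the median split's 64%.

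**5. Effect on power.** Let r be the assumed correlation of volume with TIL density. The stratified t-test is treated as a linear model with a stratum term. The effective standardized difference is 0.8/sqrt(1 - k r^2) for the split and 0.8/sqrt(1 - r^2) for continuous volume. For r = 0.5 and p = 5%, 0.8/sqrt(1 - 0.224 x 0.25) = 0.823; with continuous volume, 0.8/sqrt(0.75) = 0.924. Power uses 42 df for the split and 41 df with stratum and volume together.

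| r (assumed) | Split, 5% above | 15% | 30% | 50% | Continuous |
|---|---|---|---|---|---|
| 0.3 | 81% | 81% | 82% | 82% | 83% |
| 0.5 | 82% | 84% | 85% | 86% | 89% |

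If r = 0, the extra degree of freedom takes power from 80.06% to 80.03%.

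**6. Which read supplies the volume.** Criterion 3.1.4 gives the size decision to the local site, and footnote 25 to the study calendar agrees: "Local reading (investigator assessment) will be used to determine eligibility and for participant management". Section 11.5 adds a check at the coordinating center before randomization: "The review of the baseline neuroimaging will be performed at" that center. Section 11.1.6 has scans evaluated both locally and centrally. None of these says which read yields the cc value for the stratum, or that a volume is recorded.

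**The case against.** The case against is strong on several readings that a reader might infer, and most of it stands.

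- **That 15 cc sits near the top of what the 4 cm limit allows.** Not on the scale used to stratify: 15 cc is 45% of the 33.5 cc that a 4 cm sphere holds. A 3.1 cm sphere qualifies without being near-maximal, and a 4 cm tumor with axes at 68% of the longest qualifies without being near-spherical.
- **That the upper stratum will usually be small.** This rests on a size distribution the documents do not give. A range of 3% to 53% supports saying it may be small, and no more.
- **That the adjustment is nominal.** Not shown. With 20-30% above the cut the adjustment is real. In a simulation with a stratum effect of 1 SD and 30% above the cut, the stratified test had about 80% power and the unstratified test about 75%. A sparse stratum brings little gain but causes no bias or material loss of power: the stratified test stayed near 80% at shares from 5% to 45%.
- **That the documents contradict each other on who reads the baseline scan.** A local decision with central verification is compatible. What is missing is the source of the stratification volume.

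It is also fair to say that most of the gap to continuous volume comes from splitting at all rather than from where the cut lies. At r = 0.3 with 14% above the cut, moving it to the median would raise power only from 81.4% to 82.1%. The planned analysis correctly matches the randomization, and nothing in the documents supports a particular correlation between volume and TIL density. None of this removes the narrower point: a split discards part of the information at any share, and retaining it costs almost nothing.

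**Conclusion.** The point holds as a minor, optional improvement. The planned test is valid and unbiased, but it uses a two-level version of a measurement that must be known as a continuous value.

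Measured against splits with 5% to 50% of patients above the cut, the gain is about 1 to 2 power points if volume correlates 0.3 with TIL density and about 3 to 7 points if it correlates 0.5. It is nil if they are unrelated. These figures assume a roughly normal covariate on the analysis scale, a linear relation, and d = 0.8 on the unadjusted SD. They do not require the share above 15 cc to be known, and the documents cannot supply it.

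**What to change.** - **13.4 (and the test named in 13.3):** keep the randomization strata, and replace the stratified t-test with a prespecified ANCOVA of TIL density, suitably transformed, on group (A vs B+C), randomization stratum and continuous log baseline tumor volume.
- **5.5:** name the one baseline read that supplies the volume, how cc are derived from the scan, and whether lesions are summed. Use that same value for stratum and covariate, and record it. Section 11.5 does not itself provide for a volume measurement, so if the central review is chosen this must be added there. Align 3.1.4 and calendar footnote 25.
- **5.5 or 13.3:** state the expected share above 15 cc, if the sponsor has data on it.

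The cost is protocol and SAP wording, one recorded value per patient and one degree of freedom, worth under 0.1 power point. The model should be fixed before TIL data are seen.
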